## **5.6 Data Analysis**

All data will be entered into an SPSS database at the individual sites; de-identified data will be transferred electronically bi-weekly to the Data Coordinating Center (DCC) at the JJ Peters VAMC where it will be merged into a master database constructed by the data manager with input from the biostatistician, [name]. Tenets of our data system include double data entry, range checks and exclusion of identifiers that can be directly traced to individuals. Data are backed-up bi-weekly onto Zip drives and saved. Our computers are accessible only to authorized study personnel and are protected by a firewall and Norton antiviral software. All original forms and backup-up data will be saved in locked cabinets in locked rooms. Data analysis will be done in SPSS or SAS. Preliminary analyses will be performed by the project director, in collaboration with [name], who will perform the final runs for complex analyses such as mixed models.

#### General Approach:

Preliminary analyses including computing descriptive statistics and inspecting features and patterns of data to determine whether data transformations are necessary will be performed. We will test whether clinical characteristics of the study population, (e.g., age, sex, race, PTSD comorbidity), and other variables known to be prognostically related to the primary outcomes, are comparable between two treatment groups at baseline, using t-tests or Wilcoxon rank-sum for continuous variables, and chi-square or Fisher's exact tests for categorical variables. Groups will be considered imbalanced on variables that differ between them at p < .10 and all such imbalanced baseline prognostic factors will be included in primary analyses as control variables. Psychometric analyses will be conducted to check the properties of the scales for this sample. Outcome variables such as the Sydney and CBI will be measured at three time points for each participant. Because repeated measurements on individual subjects tend to be correlated and in some cases, the number and spacing of observations may vary among subjects, we will examine these data by graphic displays of outcome variables versus time and individual subject and mean profiles to assess the mean structure for modeling fixed effects and to examine whether there are heteroscedasticity and/or curvature in the data. Linear mixed models (LMM), generalized linear mixed models (GLMM) or generalized estimating equations (GEE) will then be used to account for dependence of repeated measures and to accommodate correlated errors, unequal correlations among time points, unbalanced data resulting from

missing data points and unequal intervals between testing occasions. Choices of variancecovariance structures to account for within-subject correlation will be made based on the AIC, BIC, or likelihood ratio statistic. All principal analyses will be conducted based on the intentionto-treat principle in which any participant randomized to a treatment arm remains in it regardless of adherence to or completion of treatment. We will measure the level of participation, and will conduct a sensitivity analysis that assesses the stability of the conclusions from this study with an intention-to-treat analysis versus an analysis that takes into account level of adherence. With multiple time points and variables representing outcomes at both the individual and couples level, the planned analyses involve multiple comparisons raise concerns about the increased likelihood that any single outcome will be found to be statistically significant based on chance alone. In order to minimize this risk, we have carefully selected a limited number of outcomes and clearly designated primary, secondary and exploratory outcomes. Our primary outcomes for the Veteran and for the caregiver are each represented by a single measure. For models evaluating the effect of treatment assignment on constructs represented by more than one measure, e.g., Veteran Emotion Regulation and Interpersonal Skills, we will employ Bonferroni's correction to adjust each observed p-value by the number of tests performed and have calculated power on this basis (see power calculations below).

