**Table 5: Veteran and Partner Assessment** 

	Pre-treatment	Post-treatment	6-month		
Veteran Assessment					
Community Integration					
Sydney Psychosocial Reintegration Scale and CRIS-	X	Χ	Х		
CAT*	^	٨	^		
Emotion Regulation/Interpersonal Skills					
DERS (emotion regulation)	X	Χ	Χ		
Duke Social Support Scale (use of supports)	X	X	Χ		
Health Behavior	X	Χ	Χ		
CES-D-10 (depression) a	X	X	Χ		
PCL-M (PTSD) Checklist a	X	Χ	Χ		
Combat Exposure Scale a	X				
PROMIS-PI (pain)	X	Χ	Χ		
ISI (insomnia)					
Service Use Checklist a	X	X	Χ		
Addiction Severity Index a	X	Χ	Χ		
Memory Compensation Questionnaire a	X	Χ	Χ		
BSI Anxiety subscale	X	X	Χ		
MINI (Axis I Disorders)	Χ	Χ	Χ		

	.,	.,		
Life Satisfaction Scale	X	X	X	
Health Risk Behavior Scale	X	X	Χ	
Neuropsychological				
Rey Auditory Verbal Learning test *	X	X	Χ	
Trail Making Test A,B *	X	Х	X	
MASC (theory of mind)	X	X	Χ	
Couples Functioning				
Dyadic Adjustment Scale*	Χ	X	X	
IRI	Χ	Χ	Χ	
CPQ	Χ	Χ	Χ	
PACT (coping flexibility)	Χ	X	X	
Post Traumatic Growth Inventory – Short Form	Χ	X	X	
CARE (relationship skills)	Χ	Χ	X	
Spouse/Partner Assessment				
Emotion Regulation/Interpersonal Skills				
DERS (emotion regulation)	Х	Χ	Х	
Duke Social Support Scale (use of supports)	Χ	Χ	Χ	
Neuropsychological				
MASC	Χ	Χ	Χ	
Caregiver Burden/Health	.,		.,	
Caregiver Burden Inventory	Χ	X	X	
CES-D-10 (depression) a	Χ	Χ	Χ	
PCL-C (trauma)				
ISI (insomnia)	Χ	Χ	Χ	
SF-8 (health) a	Χ	Χ	Χ	
Service Use Checklist a	Χ	Χ	Χ	
BSI Anxiety subscale	Χ	Χ	Χ	
MINI (Axis I Disorders)	Х	Χ	Χ	
Life Satisfaction Scale	X	Χ	Χ	
Health Risk Behavior Scale	Х	Χ	Χ	
Couples Functioning				
Dyadic Adjustment Scale	X	Χ	X	
IRI	Х	Χ	Χ	
CPQ	X	X	X	
PACT (coping flexibility)	X	X	X	
Post Traumatic Growth Inventory – Short Form	X	X	X	
CARE (relationship skills)	X	X	X	
B. I. L. C.	^		^	

**Bolded measure** indicates primary outcome measure. a covariate in model \* NINDS core test for TBI. Screening measures are described under 2avi above.

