### Tests of Specific Study Hypotheses:

### **Primary Hypotheses:**

Hypothesis 1: Veterans with mTBI treated with 6 months of multi-family group for couples (MFG-mTBI-C) will show improved community integration (primary outcome), and improved anger management and use of social support (secondary outcomes) compared with those treated in a health education group without training in communication skills or compensatory strategies; Changes in the primary study outcomes (Sydney Psychosocial Reintegration Scale) from baseline for each treatment group at each time point will be examined using paired t-tests or Wilcoxon signed-rank tests as appropriate. Differences in changes in mean Sydney scores from baseline between two treatment groups will be compared using t-tests or Wilcoxon rank-sum tests as appropriate at each time point. Linear mixed models will be used to examine changes in scales over time and to examine whether the effects of MFG-mTBI-C on the Sydney and secondary Veteran outcomes (DERS and social support scales) vary with time and study sites adjusted for the time-dependent treatment, imbalanced baseline prognostic factors (if applicable), and control variables relating to combat/ injury exposure (mechanism of injury (blast vs. other), # deployments, # TBI's and degree of exposure to war zone violence/threats). In addition, Spearman correlation coefficients will be used to assess associations of changes in the Sydney with changes in Veteran symptoms from baseline at each time point and to examine whether degree of associations increases over time among Veterans treated with MFG-mTBI-C. If significant patterns over time are observed in any of these variables, mixed models will then be used to examine the effects of the variables identified on CI change over 6 months post treatment.

Hypothesis 2: Caregivers whose Veteran spouse/partners are treated with MFG-mTBI-C will show reduced burden (primary caregiver outcome) over the course of treatment and in the 6-month follow-up period relative to caregivers whose Veteran partners are treated in a health education group. The analytic plan proposed in Hypothesis 1 will be used for assessing effects of MFG-mTBI-C on changes in the CBI.

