Secondary Outcomes: We calculated power for the Veteran secondary outcomes, AX (anger expression) and Duke (social support) scales for a two-sided, two-sample t-test, using the same assumptions for calculating primary outcomes and the observed correlation coefficients of .90 and .72, respectively for a two sample t-test, with alpha=0.025. Based on these assumptions, we have 94% power to detect an effect of .5 on the AX scale and 81% power to detect an effect of .5 on the Duke scale. Covariates: Due to the high degree of comorbidity in this cohort of Veterans, we have specified a number of variables for potential inclusion as covariates in our analytic models, should randomization result in an imbalance. These include Veteran (and where appropriate caregiver) physical health, substance use, service use (including starting and stopping treatment), level of depressive and post-traumatic stress symptoms, as well as usual sociodemographic (race/ethnicity, gender, age, SES) and military (e.g., number of deployments) variables. As noted above under General Approach, we will employ t-tests or Wilcoxon ranksum for continuous variables, and chi-square or Fisher's exact tests for categorical variables at baseline to identify any imbalance between groups on these variables, and will control for any imbalance by including variables that differentiate groups at conventional levels by including them in our analyses as covariates. However, as discussed, given random assignment of a sample of 180 to one of two treatment groups, we anticipate that few if any variables will differentiate between groups, and that our power analyses are conservative enough to accommodate inclusion of a limited number of covariates if necessary. Potential inclusion of covariates as "control variables" should be distinguished from inclusion of covariates for the purpose of testing exploratory mediating/moderating hypotheses as described under hypotheses 3 and 4 above.

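### Apart from four fixed exposure covariates, baseline significance tests between arms decide which covariates enter the primary models: this selects chance imbalance, makes the test slightly conservative and can cost power

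*Combined protocol and SAP*

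**What the plan says.** The covariate rules stand in four places.

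- **Section 5.6, General Approach.** Baseline characteristics, together with "other variables known to be prognostically related to the primary outcomes", are tested between arms. A p-value below .10 counts as imbalance, and the plan then states that "all such imbalanced baseline prognostic factors will be included in primary analyses as control variables".
- **Section 5.6, Hypothesis 1.** The mixed models for the Sydney and the secondary Veteran outcomes adjust for imbalanced prognostic factors where there are any. They also adjust, with no balance condition, for "control variables relating to combat/ injury exposure (mechanism of injury (blast vs. other), # deployments", number of TBIs and war-zone exposure. Hypothesis 2 applies the same analytic plan to the CBI.
- **Section 5.6, Covariates paragraph (after the power tables).** Physical health, substance use, service use, depressive and post-traumatic stress symptoms, sociodemographic and military variables are named for "potential inclusion as covariates in our analytic models, should randomization result in an imbalance". The entry rule here is "including variables that differentiate groups at conventional levels by including them in our analyses as covariates", which is not the p < .10 of General Approach. The paragraph adds that "we anticipate that few if any variables will differentiate between groups".
- **Section 5.1, Table 5.** CES-D-10, PCL-M, the Combat Exposure Scale, the Addiction Severity Index and other measures carry the footnote "covariate in model", with no condition attached.

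No section names the baseline value of the outcome as a fixed covariate.

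**The concern.** In a properly randomised trial, any baseline difference between arms is chance. A test of that difference says nothing about whether the variable predicts the outcome, and prediction is what makes adjustment worthwhile. A strong predictor that happens to balance is left out; a weak one that happens to differ goes in. The form of the primary model is then settled by the draw and becomes known only after the arms have been compared. At stake are precision from measures the trial already collects, and a primary model that can be stated in advance. The four statements also disagree: two thresholds are given, number of deployments is both fixed and conditional, and baseline symptom scores are flagged as covariates in one place and conditional on imbalance in another.

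**Working it through.** **Inputs from the documents.** 75 per arm (Table 4); 15% attrition (Tables 8 and 9), so 75 × .85 = 63.75, taken as 63; two-sided alpha .05; planning correlation between baseline and follow-up .5; pilot correlations .83 (Sydney) and .84 (CBI).

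**Assumed.** The share of outcome variance that the candidate covariates explain, and the number of candidates. The documents give neither.

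**1. The plan's own figure.** Power ≈ Φ(d√(n/2) − 1.96). The plan defines effect size as (mt − mc)/mc. With mt = 3.9, an effect of .5 means 3.9 − 3.9/1.5 = 1.3 Sydney points. The SD of change is not stated; the value that best fits all of Table 8 is about 2.59, so d = 1.3/2.59 = .50. At 76 per arm: .5 × √38 = 3.08, and Φ(1.12) = .87, as stated. This is an unadjusted t-test. At 63 per arm: .5 × √31.5 = 2.81, and Φ(.85) = .80. That is the reference below.

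**2. How often covariates enter.** At p < .10, each candidate enters in about 10% of trials. In simulation with one candidate the entry rate was about 10% at every outcome correlation tried (.3, .5, .7). With independent candidates, the chance that at least one enters is 1 − .9^10 = .65 for ten and 1 − .9^15 = .79 for fifteen. The list is open-ended, so either count is an assumption.

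**3. Level and power of an endpoint model.** Simulated with 63 per arm, d = 0 or .5, and 15 independent candidates of which two or three are prognostic. The rule was compared with always adjusting for the prognostic ones.

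| Share of analysed variance explained | Power lost by the rule |
|---|---|
| 3% | about 2 to 3 points |
| 12.5% | about 5 points |
| 25% | about 9 points |

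At 12.5 to 25% the rule gave 78 to 80% power and a type I error of about 4 to 4.6%. Always adjusting gave 84 to 89% and about 5%. Part of the loss arises because irrelevant covariates that enter are, by selection, correlated with treatment and widen its standard error.

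If a single candidate carries all the variance, the type I error under the rule is 4.6%, 3.8% and 3.0% at correlations of .3, .5 and .7, and the loss is about 3, 8 and 14 points. Every departure of note is below 5%.

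**4. Which share is plausible.** Suppose a covariate correlates .5 with the outcome at both visits. It then explains none of the change score. Given the baseline score, its partial correlation with follow-up is .5(1 − rho)/√(.75(1 − rho²)). At rho = .83 this is .085/.483 = .176, or 3% of the remaining variance. At rho = .5 it is .25/.75 = .333, or 11%.

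**5. Treatment-by-time contrast.** In three simulated datasets (60 per arm, three visits, complete data), adding a strong baseline covariate as a main effect left the treatment-by-time estimate and standard error unchanged to five decimals (for example .36075, SE .09995 both ways).

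**6. Baseline outcome score.** Adjusting change for baseline multiplies the SD by √((1 + rho)/2).

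- rho = .83: √.915 = .957, d = .523, .523 × 5.61 = 2.93, Φ(.97) = .83.
- rho = .5: √.75 = .866, d = .577, .577 × 5.61 = 3.24, Φ(1.28) = .90.

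Both compare with .80 unadjusted.

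**The case against.** The strongest reply has three parts.

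First, the plan is not purely data-driven. Hypothesis 1 fixes four exposure covariates, Table 5 flags PCL-M and CES-D-10 as model covariates, and the pool tested includes variables named as prognostic. This stands. A reader might infer that covariates enter only through the baseline test, that prognosis is ignored, or that baseline PTSD and depressive symptoms are certain to be left out; the text supports none of these. But a prognostic pool does not repair the rule, because the p-value still decides entry. Nor does the flag settle the symptom scores: the text below Table 5 calls the mental health and health behaviour measures potential covariates, and the Covariates paragraph makes symptoms conditional on imbalance.

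Second, a reader might infer that a data-dependent model inflates false positives. It does not: in these simulations the type I error sits at or below 5%. The cost is power.

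Third, the simulated endpoint model may not be the planned test. Section 5.6 describes t-tests or rank-sum tests of change, with no covariates mentioned, and mixed models over three visits, without saying which contrast decides the primary hypothesis. Under a treatment-by-time contrast with main-effect covariates and complete data, the loss all but vanishes. It could return with missing data, covariate-by-time terms or a baseline-adjusted endpoint model. This also stands, and it is why the loss is given as a range that reaches nil.

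**Conclusion.** The concern holds in a limited form. Outside the four fixed exposure covariates, a baseline test between randomised arms decides entry, at a threshold stated two ways and in conflict with Table 5. This selects chance imbalance and leaves the primary model open until the arms are compared. Validity is not threatened: the test is slightly conservative.

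The power cost runs from close to nil to about 9 points over the range of 3 to 25% of variance. It turns on prognostic strength and on the contrast tested, neither of which the documents settle. For an analysis of change at the pilot correlation, the low end is the more plausible. The simulations use a single follow-up and omit the four fixed covariates and clustering by treatment group.

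The only gain that rests on the plan's own correlations is from the baseline outcome score: about 3 points at the pilot value and 10 at the planning value, relative to an unadjusted change score. The change is worth making because it is cheap and fixes the model in advance.

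**What to change.** Remove the baseline tests as an entry rule and report balance descriptively. Before unblinding, fix one short list that is entered regardless of balance:

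- the baseline value of the outcome, either as a covariate or by constraining the arms to a common baseline mean in the mixed model;
- VISN, because randomisation is within VISN;
- for the Veteran outcomes, the four exposure covariates already named under Hypothesis 1, with a stated coding of injury mechanism and number of TBIs for Veterans who qualify under section 5.4 on PTSD or combat stress alone;
- one or two baseline symptom scores already collected: PCL-M and CES-D-10 for the Veteran outcomes, the partner's CES-D-10 for the CBI.

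Use baseline values only. The service-use item covers starting and stopping treatment, which can occur after randomisation. State which contrast is the primary test. Bring Table 5, General Approach, Hypothesis 1 and the Covariates paragraph into line with the list.

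The cost is a change of SAP wording and a few degrees of freedom. No new data are needed.

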Table 4: Timeline of Research Tasks

Months	Research Task
0-5	Refine manual, develop adherence scale for control condition, Train educators
	and research assistants, IRB submission, approval
4-5	Specify procedures for random assignment; blinding assessors, develop
	databases, refine recruitment procedures with study and facility staff

5-38	Enroll and study 150 cases (75 treatment, 75 control); Follow-up assessments
39-44	Complete follow-up on last cohorts' cases for 6 months
44-48	Analyze, disseminate data

Tempo: In order to study 14 groups of 3-5 couples each (7 treatment, 7 control) per VISN (3 and 5), each VISN will begin recruitment and individual sessions for two groups, one treatment, one control in study month 5, and continue to enroll and initiate treatment for two additional groups, one in each study condition, every 4-5 months until all groups have been completed and followed, in study month 44. This design will in most cases avoid a long wait for participants between randomization and starting treatment. In cases where one treatment condition becomes "filled", in order to avoid long delays and possible attrition before starting treatment, and permit both interventions to be conducted in tandem, we will allow groups with as many as 8 and as few as 3 couples. The protocol also permits an additional "Joining" session to keep early enrolled couples engaged while later-enrolled couples are being assessed and 'joined". In terms of workload, although there will be overlap between groups, the more labor-intensive work of recruiting, consenting and meeting with individual couples will overlap with the less intensive bi-monthly group meetings for the previously-enrolled two groups and will therefore be feasible.

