
Table 6: Comparison of MFG-mTBI-C and Control Treatment (GHE)

Treatment Component	MFG-mTBI-C	GHE (Control)	
Therapeutic Strategy	Skills training	Information only	
Contents	Compensation for TBI-related deficits in emotion processing, memory/planning	Building a healthy lifestyle	
Target Group	OEF/OIF/Persian Gulf Veterans with TBI/partners	All OEF/OIF/Persian Gulf Veterans/partners	
Use of Group Dynamics/ Cohesion	Social support promoted:  Entire group participates in problemsolving for each couple and gives support and encouragement	Social support minimized:  Because individual health issues are not discussed, education is general and group interaction minimized	
Therapeutic Stance	Educator stance is collaborative	Educator stance is didactic	
Room Set-up	Round table	Lecture style (all chairs face forward)	
Source of Material	Drawn from everyday problems brought in by group members	Supplied by educator	
Homework	Assigned and reviewed and the start of the following session	Handouts but not homework provided	

Table 7: Comparison of MFG-mTBI-C and Control Treatment (GHE)

Treatment Component	MFG-mTBI-C	# sessions	GHE (Control)	# sessions
Joining	Couples-tailored Education:* Normalization of couples conflict, misattribution of TBI deficits corrected.  Skills Training: Recommend 1+ compensatory strategies, basic communication training exercise.  Formulation of problems in coping & communication patterns	2(3)**	Standard Couples Intake: History of Veteran, partner and couple, focusing on current health, activities, sleep patterns, diet, medications and other health behaviors. No skills training, cognitive interventions or formulation of couples' functioning.	2(3)**
Multifamily Group Sessions	Educational Workshop: TBI: pathogenesis, behavioral sequelae, comorbidities, treatment, prognosis and family impact. Structure and function of multifamily group, how it can help.	2	Health Education Introduction: Structure and rationale for intervention. Rules of conduct. Overview of topics to be covered.	1
	Problem-solving Sessions: Skills training: Problem-solving designed to address specific problems associated with mTBI. Compensatory strategies for memory problems, planning. Disability-adapted communication training.	12	Group Health Education: Information provided to promote healthy living in areas relevant for Veterans and partners (sleep hygiene, nutrition, use of alcohol, drugs, safe exercise). Personal health concerns not discussed-referred to provider.	13

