Cross-Site Fidelity Monitoring of Educators. In Stage I of fidelity monitoring, the most experienced raters, Drs. [name] or [name] will rate every fourth MFG-mTBI-C session, for each of the first two groups at each site using the TCAS scale (5 ratings on each of 4 groups=20 tapes) to establish inter-rater reliability. They will also rate the first GHE session and two additional randomly selected sessions for the first two GHE groups at each site, to establish inter-rater reliability. In Stage II of monitoring, (i.e. after the educators have established good adherence and reliability with our expert raters), study educators will rate two randomly selected sessions from each of the 5 subsequent MFG and 5 GHE groups at each site, with each educator rating sessions from the other site (i.e., the JJP educator will rate VAMHCS sessions and vice versa). In cases where a rater observes significant departures from the MFG-mTBI-C or GHE protocols, he/she will inform [name] and the Treatment Committee. Intraclass correlations between TCAS raters will be computed at the end of years 2 and 3 on at least 10 tapes per year.

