.5	25%	90/67	0.05	.79
.6	15%	90/76	0.05	.91
.6	20%	90/72	0.05	.89
.6	25%	90/67	0.05	.87
.7	15%	90/76	0.05	.95
.7	20%	90/72	0.05	.94
.7	25%	90/67	0.05	.93

Calculated for rho = .5; Pilot rho = .833Calculated for rho = .5; Pilot rho = .839

t-test, with alpha=0.05, rho=.50 and effect sizes ranging from .5 to .7. Although attrition in the pilot study was relatively low: 10%, we have conservatively calculated power for higher rates of attrition that that observed in our pilot work: 15%, 20% and 25%, at effect sizes lower than the 1.03 effect size observed for both measures. For the Sydney, we have good power to detect an effect of .5 for Occupational activity, assuming a correlation coefficient of .5, lower than the correlation observed in the pilot study of .83 even with 2.5 times the attrition observed in the pilot study. For the CBI we have good power to detect an effect of .5, lower than the correlation observed in the pilot study of .84, even at 20% attrition, and more power at higher effect sizes or lower levels of attrition. In the unlikely scenario that a substantially lower correlation is observed (.3) along with an effect size half that observed, our power falls somewhat short of conventional standards at higher levels (25%) of attrition (i.e., .70 for Sydney and .68, with a higher correlation coefficient, lower attrition or a larger effect size we have good power to detect a medium to large effect size.

We note that a larger sample size and repeated measures at follow-up will tend to increase the correlation coefficients and reduce the variance of the change over time, most likely resulting in an increase in power. The above power calculation is based on a two-sample t-test which is the simplest form of LMM (with random intercept only) and GEE. If the imbalance between groups on key participant characteristics is minimal, as we anticipate in this randomized trial, this calculation is justified. We chose the more robust approach of using the simpler model and powering our study for a worst case scenario (compared to the effect sizes and correlations

observed in our pilot data) to cover the possibility of a more substantial imbalance, rather than basing our calculations on a more sophisticated model involving many assumptions.

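### Couples are randomised singly but treated in 28 therapy groups, and section 5.6 has no therapy-group effect, so any within-group correlation inflates type I error and overstates power for the Sydney and CBI

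*Combined protocol and SAP*

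**What the plan says.** Section 5.1 (Randomization and Maintaining Blind) randomises individual couples, 75 to each condition, within VISN. The Tempo paragraph then sets up treatment in groups: "In order to study 14 groups of 3-5 couples each (7 treatment, 7 control) per VISN", over two VISNs. It adds that "we will allow groups with as many as 8 and as few as 3 couples". The fidelity plan in section 5.1 gives the same count: the first two groups per condition, then "each of the 5 subsequent MFG and 5 GHE groups at each site", or seven per condition per site.

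In section 5.6, General Approach, the mixed models or GEE "will then be used to account for dependence of repeated measures", and "Choices of variancecovariance structures to account for within-subject correlation will be made" on AIC, BIC or likelihood ratio. Under Hypothesis 1, differences between arms in Sydney change "will be compared using t-tests or Wilcoxon rank-sum tests as appropriate at each time point"; Hypothesis 2 applies the same plan to the CBI. On power: "The above power calculation is based on a two-sample t-test which is the simplest form of LMM", with a random intercept only.

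Study site is the only grouping factor in the primary models. The hierarchical models under Hypothesis 3 serve the mediation analysis and name no therapy-group level.

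**The concern.** Couples in one therapy group share a leader, a set of members and a series of sessions. Correlation from that source arises after randomisation, so individual randomisation does not remove it. A site term does not absorb it either, because each VISN runs seven groups per condition.

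The protocol's own account makes such correlation plausible in MFG-mTBI-C. Table 6 says of that arm: "Entire group participates in problemsolving for each couple and gives support and encouragement". The health education arm (GHE) is designed to limit interaction, so correlation there may be weaker or absent.

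With positive correlation, the variance of each arm mean exceeds what the tests assume. Both primary outcomes would then have too many false positives and intervals that are too narrow. Nothing in the plan would show whether this had happened.

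**Working it through.** **Inputs.** From section 5.1: 14 groups per arm, 3 to 8 couples each, 75 couples per arm. From section 5.6: two-sided alpha .05, attrition scenarios of 15-25%, Tables 8 and 9. Assumed: ICC of .02, .05 or .10 on the change score, and 20% loss, giving 75 × .8 = 60 analysed per arm.

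**Group sizes.** 28 groups of at most 5 hold 140 couples. Enrolling 150 needs a mean of 150/28 = 5.4, so the 3-8 range will be used and sizes will be unequal.

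**The plan's power figures.** Section 5.6 defines effect size as (mt − mc)/mc, so the difference in mean change is mt × ES/(1 + ES). At ES .5 this is 3.9 × .5/1.5 = 1.3 (Sydney) and 18.0 × .5/1.5 = 6.0 (CBI). The SD of change is not stated. One fitted SD per outcome (2.59 and 12.6) reproduces all 18 cells of Tables 8 and 9 within 2 points, with no design effect. The tables are therefore independent-couples calculations. Solving the 20% attrition rows (72 per arm, power .85 and .81) gives standardised differences d = .503 and .476.

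**Type I error.** Mean analysed group size is m = 60/14 = 4.29, and the design effect is DE = 1 + (m − 1) × ICC. For equal groups, the size of the unadjusted test is about 2[1 − Φ(1.96/√DE)]. If only MFG clusters, DE is replaced by (DE + 1)/2. The simulation used unequal groups of 3-8 and 40,000 trials per setting.

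| ICC | DE | Both arms: formula | Both arms: simulated | MFG only: formula | MFG only: simulated |
|---|---|---|---|---|---|
| 0 | 1 | 5.0% | 4.9% | 5.0% | – |
| .02 | 1.066 | 5.8% | 5.8% | 5.4% | 5.4% |
| .05 | 1.164 | 6.9% | 7.3% | 6.0% | 5.8% |
| .10 | 1.329 | 8.9% | 9.8% | 6.9% | 7.3% |

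**Power of a correctly sized test.** Effective n = 60/DE, noncentrality = d√(n_eff/2), and df = 28 − 2 = 26. If only MFG clusters, the variance of the contrast is (DE + 1)/60, with Satterthwaite df of about 41, 39 and 35.

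| Setting, 60 per arm | Sydney | CBI |
|---|---|---|
| No clustering, 118 df | .78 | .74 |
| ICC 0, 26 df | .76 | .71 |
| Both arms, ICC .02 / .05 / .10 | .73 / .69 / .63 | .68 / .64 / .59 |
| MFG only, ICC .02 / .05 / .10 | .75 / .73 / .70 | .71 / .69 / .65 |

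The fall from the tabulated .85/.81 to .78/.74 is not clustering. It comes from a separate mismatch: the tables start from 90 per arm, while the plan enrols 75.

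**Would a simple group intercept be enough?** Data were simulated with baseline and post scores, 28 groups of 5, a group effect arising only after baseline, and ICC .10 on change. In three fitted datasets, a mixed model with a time-constant group intercept gave the same arm-by-time standard errors as the plain t-test on change: .1666, .1750 and .1441. The group-level standard errors were .1747, .2162 and .1972. Over 400 trials the plain t-test rejected 9.3% and the group-level test 4.5%. A time-constant intercept therefore leaves the tested contrast uncorrected.

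**The case against.** - **Power.** The lower figures belong to an adjusted test that the plan does not use. The planned t-test itself would still reject about .77/.76/.74 of the time for the Sydney at ICC .02/.05/.10, against .78 at ICC 0. This is correct, but that rejection rate is bought with a true alpha above 5%. Part of the loss is also degrees of freedom alone (.78 to .76 at ICC 0).
- **Margin.** Section 5.6 powers at a baseline-to-follow-up correlation of .5, against pilot values of .83 and .84. If the variance of change scales as 2(1 − rho), power at ICC .10 with 26 df is .84/.80 at rho .7 and about .98/.97 at the pilot values. If the pilot correlations hold, power is ample. For a given ICC, though, rho does not alter the type I error.
- **Size.** Every ICC is assumed. In the MFG-only case, inflation at .02 is slight. MFG and GHE groups start in pairs within a VISN, so a cohort component shared across arms would partly cancel. If half the group variance were shared (an assumption), type I error with both arms clustered would be about 5.5/6.0/6.3%. Call-in attendance may weaken clustering further. These points bear on size, not direction.
- **Remedy.** With about 4.3 analysed couples in 14 groups, the ANOVA group-variance estimate within one arm is zero or negative about 46/36/23% of the time at ICC .02/.05/.10, and an adjusted model then collapses to an unadjusted one. The full model with arm-specific variances was not simulated. This is a reason to prespecify how boundary estimates are handled, and does not justify omitting the term.

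**Conclusion.** The concern holds. The plan treats couples who share a therapy group as independent in its tests, models and power for both primary outcomes, and no other section supplies the missing term.

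The consequence is conditional. At an ICC of zero the planned tests are valid. Over the assumed range .02-.10, the nominal 5% test has a true size of about 5.4% to 9.8%, depending on the ICC and on whether one arm or both cluster. Power of a correctly sized test at the effect labelled .5 is .63-.75 (Sydney) and .59-.71 (CBI) under the plan's working correlation of .5. These figures rest on 60 analysed per arm, independent groups, and effect sizes solved from Tables 8 and 9.

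The omission itself is certain; its size is not known. It should be corrected before unblinded analysis because the error runs towards declaring efficacy, and prespecification removes a later choice between clustered and unclustered results.

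**What to change.** In section 5.6:

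1. Make the confirmatory analysis of the Sydney and CBI, and likewise of the secondary outcomes, a mixed model in which group clustering acts on the tested contrast. Either (a) model change or follow-up score with baseline as covariate and a therapy-group random effect, or (b) keep the repeated-measures model and add a therapy-group-by-time (post-baseline) random effect. State that a time-constant group intercept alone does not correct the arm-by-time test.
2. Let the group variance differ by arm, use Kenward-Roger or Satterthwaite degrees of freedom, and say what is done when a variance estimate is zero.
3. Keep couples who never attend in their assigned therapy group if they have one; otherwise enter them as singletons.
4. Make the plain t and rank-sum tests descriptive.
5. Restate power at 75 per arm for ICC .02-.10, and report the estimated ICC by arm.
6. State as a limitation that each educator delivers one intervention, so educator effects cannot be separated from treatment within a site. A group term does not solve this.

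**Cost.** SAP wording and one added random effect. No new data are needed, since the tracking database in section 5.1 already reports by therapy group. Group codes must be linked to the outcome data, and because groups are nested in arm, the codes need the same blinding safeguards as the treatment field. Intervals will be wider, degrees of freedom fewer and stated power lower; at ICC 0 the power loss is about .02 to .03.
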